### Data processing and analysis:

The data obtained in the tests will be analysed using Statistical Package for Social Science (SPSS) (IBM SPSS ver.26). For parametric data, paired sample t test will be used. Wilcoxon signed rank test will be used to analyse the data sets if they are non-parametric. The alpha level will be set at 0.05 for all statistical tests.

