# Serum myokine evaluation

Phlebotomy (5ml) will be performed on the day before PEMF treatment, and at 2-, 3-, 6- and 12- months after commencement of treatment. The serum will be prepared by centrifugation and kept in a -800 freezer until use. Quantitative analysis for myokines and proteins related to muscle metabolism will be performed by Human Myokine Magnetic Bead Panel (Millipore) with Bioplex-200 bead-based suspension assay system (LKSIHS core facilities), or enzyme-linked immunosorbent assay (ELISA). These include Brain-derived neurotrophic factor (BDNF), Fibroblast growth factor-21 (FGF-21), Interleukin-6 (IL-6), IL-15, Irisin, Myostatin (MSTN)/GDF8, Insulin-like growth factor 1 (IGF-1), FGF-2, IL-8, Follistatin, Musclin, Myonectin, Decorin, Meteorinlike, Osteopontin, Secreted protein acidic and rich in cysteine (SPARC), Klotho, Procollagen type III N-terminal peptide (P3NP), and C- terminal of troponin T1 (TNNT1).

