## Follow up time points

Subjects with OA knee will be recruited into this randomized controlled trial. Baseline assessments including KOOS, IPAQ, muscle strength, posture control and serum markers will be taken before PEMF treatments, and same set of measurements will be monitored at 1- and 2- months after the commencement of PEMF, and at 3-, 6- and 12- months after finish the PEMF intervention if possible.

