## Sample size calculation:

KOOS Score will be employed as primary outcome for sample size estimation. The minimal clinically important change has been determined as 10 for KOOS (21). A repeated ANOVA will be used to compare KOOS scores, IPAQ, muscle strength, posture control and serum markers before PEMF treatment and at 1-, 2-months after the commencement of PEMF treatment, and at 3-, 6- and 12- months after finish the intervention. When the sample size is 34 per groups with 6 repeated measurements, a one-way analysis of variance will have 95% power to detect at the 0.05 level and change of 10 with a standard deviation of 15 KOOS score (22). An additional 35% will be added to account for possible attrition. Thus, 110 (55x2) subjects will be recruited in total.

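### A flat 0.05 for every test leaves the 19-analyte serum panel without error control: about one false positive is expected if PEMF changes none of the markers

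*Protocol*

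**What the plan says.** Four sections of the protocol bear on this.

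- **Data processing and analysis** names the paired t test, with the Wilcoxon signed rank test as its non-parametric counterpart, and then sets one rule: "The alpha level will be set at 0.05 for all statistical tests".
- **Serum myokine evaluation** says "Quantitative analysis for myokines and proteins related to muscle metabolism will be performed". It names "Brain-derived neurotrophic factor (BDNF), Fibroblast growth factor-21 (FGF-21), Interleukin-6 (IL-6), IL-15, Irisin, Myostatin (MSTN)/GDF8, Insulin-like growth factor 1 (IGF-1), FGF-2, IL-8, Follistatin, Musclin", then "Myonectin, Decorin, Meteorinlike, Osteopontin, Secreted protein acidic and rich in cysteine (SPARC), Klotho, Procollagen type III N-terminal peptide (P3NP", and finally TNNT1. Blood is drawn the day before treatment and "at 2-, 3-, 6- and 12- months after commencement of treatment".
- **Follow up time points** puts serum markers in the baseline set and says the "same set of measurements will be monitored at 1- and 2- months after the commencement of PEMF". Three further visits follow, counted from the end of the intervention and held where possible.
- **Sample size calculation** says "A repeated ANOVA will be used to compare KOOS scores, IPAQ, muscle strength, posture control and serum markers" at baseline and five later times. KOOS is the only outcome it calls primary.

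No section gives the panel a role, a lead analyte, a testing order or an error rate of its own.

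**The concern.** A per-test level of 0.05 applied to a long list of markers gives each marker its own full 5% chance of a false signal. Multiplicity for secondary biomarkers is often left to the SAP, and silence here would be no finding. This protocol is not silent. It fixes the level for every test, and it lists serum markers beside KOOS in the same planned analysis without setting them apart.

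What is at stake is how a positive myokine result would be read. The Background describes muscle as the route by which regenerative agents are delivered, and the Intervention section justifies the regimen partly by myokine release. One or two analytes below 0.05 could easily be presented as support for that mechanism, when about that many are expected by chance alone.

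**Working it through.** **Inputs.** The per-test level is 0.05 (Data processing and analysis). The protocol states no panel-wide error rate, so there is no figure of its own to reproduce.

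**Number of analytes** (Serum myokine evaluation). BDNF to musclin is 11, myonectin to P3NP is 7, and TNNT1 is 1: 11 + 7 + 1 = 19. The list is worded as open-ended, so 19 is a minimum.

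**Number of tests.** Three readings are possible:

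- One repeated ANOVA result per analyte (Sample size calculation): 19 tests.
- A paired test against baseline at each of the four later draws in Serum myokine evaluation: 19 × 4 = 76 tests.
- The same at the five later times in Follow up time points: 19 × 5 = 95 tests.

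**Expected false positives with no true effect** = number of tests × 0.05. Correlation does not change this figure.

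- 19 × 0.05 = 0.95
- 76 × 0.05 = 3.8
- 95 × 0.05 = 4.75

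**Chance of at least one false positive, independent tests** = 1 − 0.95^k.

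- k = 19: 1 − 0.95^19 = 62.3%
- k = 76: 1 − 0.95^76 = 98.0%
- k = 95: 1 − 0.95^95 = 99.2%

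**Allowing for correlation.** The protocol gives no correlations, so these are assumed. Multivariate normal test statistics were simulated under no effect (20,000 runs, two-sided 0.05, equal correlation between all markers and between all visits). The chance of at least one false positive was:

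| Between-marker correlation | 19 tests | 76 tests, between-visit correlation 0.3 | 0.5 | 0.7 |
|---|---|---|---|---|
| 0.3 | 52.1% | 93.8% | 92.0% | 86.9% |
| 0.4 | 46.5% | 90.5% | 88.1% | 82.5% |
| 0.5 | 40.6% | 86.5% | 82.6% | 76.4% |
| 0.7 | 27.8% | 71.0% | 65.9% | 58.1% |
| 0.8 | 21.6% | 60.5% | 55.2% | 47.9% |

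On the 19-test reading, the chance drops below one half once the between-marker correlation passes about 0.3 to 0.35. On the 76-test reading, it stays above one half except near 0.8 between markers with 0.7 between visits.

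**What these rates assume.** Each test is taken to have a true 5% error rate for an effect of PEMF. A paired test looks at change over time, not at PEMF against sham, so ordinary change over time could make it significant with an inert device. For paired tests the rates are therefore not upper bounds, and no multiplicity adjustment removes that problem.

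**The case against.** The strongest objection is that a 0.05 level does not rule out adjustment. Bonferroni or Benjamini-Hochberg adjusted p-values are also compared with 0.05, and an SAP that is not shown may add such control. This stands in part: the sentence does not forbid adjustment. But its natural reading is that each test is judged at 0.05 as it comes, and nothing in the protocol qualifies it.

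A second objection concerns the count. The only sentence that names a test for serum markers names a repeated ANOVA, which may mean as few as one test per analyte. The section with the paired tests mentions neither myokines nor visits. This stands: 19 is the floor, and 76 or 95 is one reading each.

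Three stronger conclusions are tempting, and the documents do not support them:

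- **That a false myokine response is more likely than not.** This holds for 19 independent tests and for most correlations with 76 tests. It fails for 19 tests at moderate correlation, and the protocol fixes neither the count nor the correlation.
- **That the trial's conclusion would rest on the panel.** The Objective is knee pain, the Hypothesis names quadriceps strength, and myokines appear in the rationale but not as a decision rule.
- **That the primary analysis is compromised.** Nothing about the panel alters the KOOS test.

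Finally, unadjusted testing of a panel plainly labelled exploratory would be acceptable. That is true, but the protocol gives no such label.

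**Conclusion.** The point holds as a minor one. As written, the protocol applies 0.05 to each of at least 19 serum analytes, with no exploratory label, lead marker or error control. The firmest figure is 0.95 expected false positives over 19 tests with no true effect, because it does not depend on correlation. The chance of at least one is 62% under independence and about 52% to 28% at assumed between-marker correlations of 0.3 to 0.7, far above 5% throughout. Testing at every draw raises the expected number to 3.8 (76 tests) or 4.75 (95 tests), but the sections disagree on visits and on the test, so neither count can be taken as the plan. The consequence is confined to claims of a myokine response.

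**What to change.** Make three changes before unblinding, in the protocol or in an SAP that expressly overrides the blanket sentence:

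1. Limit the rule so that unadjusted 0.05 applies only to the primary KOOS comparison. If no document yet says which KOOS score and visit form that comparison, name them here.
2. Compare the 19 analytes between PEMF and sham, not by paired tests within an arm, at one named visit with Benjamini-Hochberg control at 5%. Two months is a natural choice because both schedules count it from the start of treatment.
3. Report other visits and other markers as exploratory estimates with confidence intervals.

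No extra participants, samples or assays are needed, and the computation is trivial. The cost is power for any single analyte: one that stands alone would need p at or below 0.05 / 19 = 0.0026. If the sponsor does not intend any confirmatory myokine claim, labelling the whole panel exploratory is a simpler alternative, still with the comparison made between arms.

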# Potential pitfall and contingency plan:

Patients that are potentially intolerable for magnetic low-field magnetic stimulation or trigger discomfort will not be included in our study during screening. If the patient record did not indicate any potential adverse reaction to the PEMF treatment and experience such a situation during the intervention, the patient would be immediately removed from the study in their best interest to safeguard their health. All staff operating the PEMF would have thorough training on the operation of the machine and familiarize themselves with the troubleshooting scheme. Study personnel would indicate and explain to patients during recruitment about the intervention duration and frequency to stress the importance of compliance, accompanied with frequent reminders to participants. In the case of patient non-compliance, study personnel

would remove the patient from the study only when multiple failed attempts to contact and convince the patient occurs.

